4.2 Outcomes

Primary endpoints:

1. Proportion of lung cancers detected with different risk models

To address the suitability of different inclusion methods for identifying the high-risk population for screening, the PLCO_M2012 model and the NELSON inclusion criteria will be compared primarily for the positive predictive value of lung cancers detected within the study population after 2 screening rounds.

Key-Secondary endpoints:

Additionally, the PLCO_M2012 model and the NELSON inclusion criteria will be compared in a hierarchical order regarding the key secondary endpoints:

1. Proportion of individuals selected for screening within the high-risk study population
2. Proportion of lung cancers detected with different inclusion methods (NELSON vs. PLCO) within the overall study population after 5 years
3. Proportion of lung cancers detected within the high-risk population
4. Sensitivity within the overall population after 5 years.

5. Specificity within the overall population after 5 years.

Secondary endpoints:

6. **Rate of initiation of cardiovascular treatments** (in particular lipid-lowering) in the calcium score reporting group vs. the non-reporting group after year 1 of study.
7. **Efficiency of nodule management algorithms:** Based on the two alternative management algorithms (LungRads1.1 alone or LungRads1.1 + PanCan/AI) participants are sorted into three management groups: (a) next surveillance scan, (b) early recall scan, or (c) diagnostic evaluation recommended. For one algorithm to be more efficient, the following criteria must both be fulfilled
 - i. The number of participants without cancer sorted in the category (a) is higher AND
 - ii. The number of participants with lung cancer sorted into category (b) or (c) is higher.
8. **Success of screening program.** Based on all individuals enrolled. Definition of success is calculated using:
 - a. Response rate (1. Respondents to questionnaire / invitation: those who send their smoking history & other relevant data; 2. among the above respondents, those who are eligible by one of the two criteria, or both; 3. those who are eligible, and actually take part in the screening), number of drop-outs, effectiveness of patient recruitment via mailings vs. GPs referrals (individual response rates)
 - b. Reliability of PLCO risk scoring (self-reported vs. on site assessment)

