6. STUDY CONDUCT AND REGULATORY DETAILS

6.1 Data Management

6.1.1 Study Flow Chart and Plan

* Follow-up schedule

LungRADS Categories:

- 1, 2: 1 year LDCT
- 3: 6 months LDCT; VDT assessment
- 4a: 3 months LDCT; VDT assessment
- 4b, X: MDT, tissue sampling depending on the probability of malignancy and comorbidities.

Figure 1: Flow diagram of the HANSE study.

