- Non-qualifying subjects (who did not meet the NELSON inclusion criteria or PLCO criteria) will be asked to volunteer by contributing long-term outcome data informing of the development of lung cancer or death from lung cancer. In addition NELSON and PLCO non-qualified subjects with a smoking history, who volunteered to participate in the HANSE study, will be contacted via mail after 5 years to inquire if they developed lung cancer in the time between their recruitment and present. Non-responders will be followed by local cancer registries and by phone.

2. **LDCT - 1. Screening round**

- **Lung function test:** All included participants will receive a lung function test prior to undergoing LDCT.
- **Cardiovascular health:** All participants will be questioned whether they receive treatment for any cardiovascular conditions. Blood pressure, heart rate and BMI data (height and weight) will be obtained.
- Assessment of current **COPD treatment medication.**
- **Randomization:** Subjects included in the screening study will be randomized prior to receiving the initial LDCT scan. Randomization will not affect the procedure and the schedule of the cancer screening process but only determine the allocation of the participants of the coronary calcium score and emphysema score to the reporting and the non-reporting group. Randomization ratio of 1:1 and a 2-factorial design ($\frac{1}{4}$ calcium score only; $\frac{1}{4}$ emphysema score only, $\frac{1}{4}$ both; $\frac{1}{4}$ none) will provide equally sized groups of patients in both groups including age (5 year groups) and sex stratification .

Lung LDCT assessment:

- **Standardized and quality-assured image analysis** will be conducted using state-of-the-art artificial intelligence (AI)-based detection and nodule measurement software (Coreline) to support the radiologist. CT assessment of lung nodules will be performed according to LungRADS 1.1 criteria (see Appendix), as well as volume doubling time according to the European position statement on lung cancer screening (14).
- Inspection of **lungs for nodules** will be carried out for all subjects, independent of the assigned groups (reporting or non-reporting).
- An independent 2nd read by an additional radiologist using the same reading software algorithm will be performed.
- Subjects with no nodules or those of LungRADS grades 1, 2, 3, 4a will be scheduled for follow-up scans at intervals according to LungRADS schedule (see Appendix).

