- **Assessment of smoking status:** Success of the smoking cessation program will be evaluated using a questionnaire, combined with a urine cotinine check (in quitters).
- **Initiation of COPD treatment:** Assessment of COPD treatment initiation during the study.
- **Consequences of screening:** Questionnaire 'Consequences of Screening' as above.

2. Evaluation

Lung cancer screening:

- The percentage of subjects receiving an adequate low-dose CT scan according to DRG guidelines will be assessed.
- For all included participants, detection rate of lung cancers will be evaluated and categorized according to LungRADS 1.1 categories.
- Detected (proven by histopathology) lung cancers will be categorized whether they were predicted by PLCO or NELSON or both. Statistical analysis will reveal potential advantages of either risk scoring methodology.
- A retrospective analysis will compare this algorithm to the PanCan nodule algorithm vs. AI for management efficiency. Based on the two alternative management algorithms patients are sorted into three management groups: (a) next surveillance scan, (b) early recall scan, or (c) diagnostic evaluation recommended. For one algorithm to be more efficient, the following criteria must both be fulfilled
 - The number of patients without lung cancer sorted in the category (a) is higher AND
 - The number of patients with lung cancer sorted into category (b) or (c) is higher.

Coronary calcium score / cardio-vascular treatment initiation:

- At the 1-year follow-up visit, the rate of initiation of cardiovascular treatment (in particular lipid-lowering) will be determined, together with BMI, and blood pressure data. Data for the calcium score reporting group will be compared to those of the non-reporting group.

Smoking cessation:

- Success of smoking cessation counseling will be based on the number of participants quitting (% quitters) within study period.
- Allocation of the participants to the different experimental groups will allow determining the influence of 'reporting' of prognostic markers (percent emphysema and coronary calcium score) on smoking cessation.

All methods will be performed according to study site SOPs.

CT analysis software (Coreline) specifications:

1. Viewer function

- LCS (Lung Cancer Screening) viewer functions

- Image display with axial, sagittal and coronal images and 3D rendering.
- Virtual slice thickness control display function for MPR (Multi-Planar Reformat) images.

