- Semi-automatic nodule segmentation and measurement.
- Follow-up nodule comparison, using automatic nodule position registration.
- Quantitative feature calculation from the nodule segmentation.
- Calculation of VDT (volume doubling time) and cancer-risk probability based on PANCAN model (Brock model).
- Structured reporting UI based on Lung RADS v1.1, with incidental findings (S Modifier) (Can be modified to conform to German requirements)
- Form-based report generation

- LAA (Lower Attenuation Area) viewer functions

- Lobe-based quantitative emphysema analysis, such as LAA-950HU and Perc15.
- Image display of axial, sagittal, coronal and 3D rendering, with LAA mask overlaid.
- Bull's eye chart for displaying LAA distribution in lobes, which are automatically segmented.
- Histogram analysis of lung parenchymal densities.
- Form-based report generation

- CAC (Coronary Artery Calcification) viewer functions

- Automatic calcification labeling and manual correction.
- AGATSTON scoring and isotropic volume scoring.
- Form-based report generation

- Automatic processing server (APS) engines

- Lung nodule detection engine (CADe, for research purpose only till CE certification)
- Lung/lobe segmentation engine for automatic nodule position determination.
- LAA analysis engine
- CAC analysis engine

- Worklist functions

- Display the important results in separate columns; (Lung-RADS category, LAA-950HU, CAC, etc.)
- Workflow management to enable double-reading capability.
- Automatic notification of high-risk (critical) reading results.
- Exporting results in CSV format (MS-Excel compatible)

2. Central registry function

- Anonymization of uploaded patient data.
- Web-based questionnaire (Specific requirements must be determined.)
- Collects all the reading results in the CLOUD database.
- CT dose management, using dose report from CT devices.
- Dashboard view to display all participating hospitals' information (charts and tables).

3. Additional function support further research work

- Radiomics feature generation from the segmented nodules.
- Exporting all the collected information in CSV format (MS-Excel compatible).
- Exporting nodule segmentation masks.
- Interface with 3rd-party research modules, such as nodule malignancy estimation.

4. Function be customized in the preparation phase of the HANSE study

- German language support.
- Customization to reflect German workflow.
- Customization of structured reporting for incidental findings.

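### In secondary endpoint 7, nothing protects the LungRADS-alone comparator from the PanCan probability calculated in the same reading viewer

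*Protocol*

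**What the plan says.** Protocol section 4.2, secondary endpoint 7, sets up a paired comparison: "Based on the two alternative management algorithms (LungRads1.1 alone or LungRads1.1 + PanCan/AI) participants are sorted into three management groups". One algorithm counts as more efficient only if two conditions both hold: "The number of participants without cancer sorted in the category (a) is higher AND" "The number of participants with lung cancer sorted into category (b) or (c) is higher". Sections 5.1.2 and 6.1.2 (Evaluation) repeat these conditions. Section 6.1.2 adds the timing: "A retrospective analysis will compare this algorithm to the PanCan nodule algorithm vs. AI for management efficiency". The algorithm used live is LungRADS 1.1 with volume doubling time.

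For the read itself, section 6.1.2 (Lung LDCT assessment) provides "artificial intelligence (AI)-based detection and nodule measurement software (Coreline) to support the radiologist". A second radiologist reads independently with the same software. The software specification later in 6.1.2 lists, among the functions of the lung cancer screening viewer, "Calculation of VDT (volume doubling time) and cancer-risk probability based on PANCAN model (Brock model" and, as the next item, "Structured reporting UI based on Lung RADS v1.1, with incidental findings (S Modifier".

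The objective served is additional objective 4 in section 2.2, that adding PanCan/AI to LungRADS increases efficiency. Section 5.2.2 treats all secondary parameters as exploratory.

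**The concern.** The two sortings are meant to differ only in whether PanCan (or AI) was used. If the PanCan figure is in view while the category is chosen, a borderline nodule may be placed where PanCan would have placed it. That participant then counts as already re-sorted under LungRADS alone, and the comparison no longer isolates what PanCan adds.

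Two things depend on this: additional objective 4, and the nodule management component of the cost-effectiveness model, which is to be built on the study's data (4.2, endpoint 12; 6.1.2). The primary comparison of NELSON and PLCO does not use this sorting.

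**Working it through.** The protocol gives no sample size, expected count or power for this endpoint, so there is no figure to reproduce. The check has two parts.

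**1. Is the comparator kept apart from PanCan?**

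- What the endpoint needs: a sorting by LungRADS 1.1 alone (4.2, 5.1.2, 6.1.2 Evaluation).
- Where the category is made: in a read supported by the Coreline software, with a LungRADS reporting form in its viewer (6.1.2).
- Where PanCan is calculated: in the same viewer (6.1.2, software specification, item 1).
- Whether another read is free of it: none is stated to be, since the second read uses the same software.
- Whether an order of steps, masking or lock is stated: no.
- Whether the retrospective label settles it: no. It dates the analysis, but does not say that the live category was assigned without sight of PanCan.

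The route for contamination is therefore open. Whether it is used cannot be read from the protocol.

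**2. Which way would a bias run?**

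Among participants without cancer, let D_N be the number whom PanCan would truly move into category (a) and U_N the number moved out of it. Among participants with cancer, let U_C be the number moved from (a) into (b) or (c) and D_C the number moved back. Let f_U and f_D be the shares of upward and downward moves that readers have already made in the recorded LungRADS category. The sorting with PanCan is taken as unchanged, and each share as the same for participants with and without cancer. Then the observed differences (with PanCan minus alone) are:

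- criterion i: (1 − f_D) × D_N − (1 − f_U) × U_N
- criterion ii: (1 − f_U) × U_C − (1 − f_D) × D_C

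If f_U = f_D, both differences shrink by the same factor and keep their sign until they reach zero. If the shares differ, they need not shrink. The counts below are invented to show direction only; none comes from the protocol.

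| D_N, U_N, U_C, D_C | f_U | f_D | Criterion i | Criterion ii | PanCan passes both |
|---|---|---|---|---|---|
| 200, 50, 5, 1 | 0 | 0 | 200 − 50 = +150 | 5 − 1 = +4 | yes (truth) |
| same | 0.5 | 0.5 | 100 − 25 = +75 | 2.5 − 0.5 = +2 | yes |
| same | 1 | 1 | 0 | 0 | no |
| same | 0.5 | 0 | 200 − 25 = +175 | 2.5 − 1 = +1.5 | yes |
| same | 0 | 0.5 | 100 − 50 = +50 | 5 − 0.5 = +4.5 | yes |
| same | 1 | 0 | 200 − 0 = +200 | 0 − 1 = −1 | no |
| 150, 200, 5, 1 | 0 | 0 | 150 − 200 = −50 | 5 − 1 = +4 | no (truth) |
| same | 0.5 | 0 | 150 − 100 = +50 | 2.5 − 1 = +1.5 | yes |

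Equal absorption pulls both criteria towards zero. If only upgrades are absorbed, criterion i is overstated and criterion ii understated; if only downgrades are absorbed, the reverse holds. In the last pair of rows, a PanCan algorithm that truly fails comes out as passing.

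**The case against.** The strongest reply is that a list of software functions is not a reading procedure. Where the protocol describes the read (6.1.2 and the appendix on nodule growth), it relies on LungRADS 1.1 criteria and volume doubling time, and it leaves PanCan to a retrospective analysis. Site SOPs, which are not shown, may set an order of reading. This stands as far as it goes: the protocol does not show that readers see PanCan first or act on it. It does not show that they cannot, and the comparator depends on that.

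A second reply is that a LungRADS-alone sorting could be re-derived later from the nodule measurements and segmentations the software stores and exports, under rules set in the statistical analysis plan. This stands in part. Categories that follow from measurements could largely be rebuilt. Where assignment rests on the reader's judgement, as may be so for 4X, what the reader would have chosen without PanCan may not be fully recoverable.

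Three stronger readings are tempting, and the documents do not support them.

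- A reader might infer that the added value of PanCan is understated. The direction depends on which moves are absorbed, as the working shows.
- A reader might take the flow chart in 6.1.1, "4b, X: MDT, tissue sampling depending on the probability of malignancy and comorbidities", as a second route for PanCan. That step follows after the category has been assigned, and the probability it mentions is not tied to PanCan.
- A reader might count the interface to outside malignancy-estimation modules as part of the reading viewer. The specification lists it under item 3, as support for further research.

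**Conclusion.** The point holds as a gap in the design of an exploratory endpoint. The LungRADS-alone category is not protected from PanCan, so the efficiency comparison may be biased: towards no difference if readers absorb upward and downward moves about equally, and otherwise in either direction for each criterion. No size can be given, because the protocol has no figure for how often readers would act on PanCan, and the endpoint compares counts without a stated effect or precision target.

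The conclusion assumes that the live category is recorded in the specified viewer and that no unseen SOP already hides PanCan until it is saved. It is a cheap improvement that protects a named objective, and it does not threaten the trial's main result.

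**What to change.** Item 4 of the software specification in 6.1.2 already plans customisation of workflow and structured reporting before the study. Within that work, have the viewer store and time-stamp the LungRADS category of each read before it displays any PanCan or AI malignancy probability. State in 4.2, 5.1.2 and 6.1.2 (Evaluation) that this stored category is the LungRADS 1.1 alone sorting.

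The probability remains available once the category is locked, so the change concerns only the order of display and recording and leaves management as it is. The cost is a small configuration change, one stored field, one extra step in each read and a sentence in each of the three sections. It needs to be in place before the first read.

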OUTCOME(S)	
Primary endpoint: Positive predictive value (PPV) for lung cancer detection with different inclusion methods (NELSON vs. PLCO) after 2 screening rounds.
 
Secondary endpoints:
 
Key secondary endpoint(s):
 
 1. Proportion of individuals selected for screening within the high-risk population 2. Proportion of lung cancers detected with different inclusion methods (NELSON vs. PLCO) within the overall study population after 5 years 3. Proportion of lung cancers detected with in the high-risk population after 5 years 4. Specificity within the overall population after 5-year follow-up 5. Sensitivity within the overall population after 5-year follow-up 
Secondary endpoints:
 
 1. Rate of initiation of cardiovascular treatments (in particular lipid-lowering) in the calcium score reporting group vs. the non-reporting group after year 1 of study. 2. Efficiency of nodule management algorithms (LungRads1.1 + PanCan) will be evaluated according to 
 - The number of patients sorted in the category (a) "Next surveillance scan" AND - The number of patients with lung cancer sorted into category (b) "early recall scan", or (c) "diagnostic evaluation". 3. Success of screening program. Based on all individuals enrolled. Definition of success is calculated using:

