2.2 Secondary Objective(s) & Hypothesis(es)

Key-Secondary Objectives:

The PLCO_{M2012} model and the NELSON inclusion method will be compared

(ii) secondarily to the primary objective regarding the following hierarchically ordered key-secondary endpoints:

1. Proportion of individuals selected for screening
2. Proportion of lung cancers detected
3. Sensitivity and specificity of the scores in cancer detection

Secondary Objectives:

The main secondary objectives of this trial is to document that:

1. Reporting of the coronary artery calcium score from low dose computed tomography (LDCT) data will lead to an increase in the rate of preventive cardiovascular treatments and reduced cardiovascular mortality.

Additional objectives are to show that:

1. Effective smoking cessation counselling is implemented as part of the screening program (urine cotinine check in quitters).
2. CT derived information on tobacco related lung destruction, such as emphysema, may influence the smoking cessation rate.
3. Structured reporting of clinically relevant non-cardiac incidental findings, e.g., emphysema or lung fibrosis, will lead to early detection and improved management of diseases.
4. Adding the PanCan algorithm/AI to the LungRads1.1 algorithm for nodule management increases the efficiency.
5. Assessment of various blood-based or exhalation-based biomarkers may provide additional translational information in positive LDCT cases with subsequent biopsy, which may have an impact on the effectiveness of the LDCT test.
6. Cost effectiveness analysis on recruiting strategies, risk models used, effectiveness on smoking cessation and cardiovascular mortality is implemented.

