For testing the null-hypothesis of no difference between the risk scores regarding the proportion of individuals selected for screening, McNemar's Test will be used.

Description of the primary analysis and population:

The primary analysis will be conducted of all volunteers within the overall study population after 2 LDCT screening rounds.

5.1.2 Secondary Objective(s): Calculation of Epidemiological Measure(s) of Interest (e.g. hazard ratios, incidence rates, test/retest reliability)

1. Rate/rate ratio of initiation of cardiovascular treatments (in particular lipid-lowering) in the calcium score reporting group vs. the non-reporting group after year 1 of study:

2. Efficiency of nodule management algorithms:

Based on the two alternative management algorithms (LungRads1.1 alone or LungRads1.1 + PanCan) patients are sorted into three management groups: (a) next surveillance scan, (b) early recall scan, or (c) diagnostic evaluation recommended. For one algorithm to be more efficient, the following criteria must both be fulfilled

- i. The number of patients without cancer sorted in the category (a) is higher AND
- ii. The number of patients with lung cancer sorted into category (b) or (c) is higher.

3. Success of screening program. Based on all individuals enrolled. Definition of success is calculated using:

a. Response rate (number of responses/overall number contacted), number of drop-outs, effectiveness of patient recruitment via mailings vs. GPs referrals (individual response rates)

b. Percentage of subjects meeting all inclusion/exclusion criteria

c. Repeatability of the PLCO score

d. Percentage of subjects receiving an adequate low-dose CT scan according to DRG guidelines (number of diagnostic CTs/number of all CTs)

4. Quality of screening program.

a. CT reading performance (2nd reader vs. CAD vs. AI)

b. Frequency of detection and management of incidental findings from low dose chest CT (emphysema, coronary heart disease, etc.)

c. Subsequent identification of biomarkers with predictive value / correlation with positive LDCT findings / cancer risk

5. Smoking cessation

a. Success of smoking cessation counseling based on number of participants quitting with or without revealing additional health risks (emphysema score, coronary calcium score or both).

6. Blood-based and exhalation- based biomarkers

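### The rule for calling one nodule-management algorithm more efficient needs only two paired counts to be higher by any amount, so chance alone can meet it (exploratory endpoint).

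*Protocol*

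**What the plan says.** Section 4.2 of the Protocol, secondary endpoint 7, sorts each participant by two alternative algorithms (LungRADS 1.1 alone, or with PanCan/AI added) into (a) next surveillance scan, (b) early recall scan or (c) diagnostic evaluation. It then states: "For one algorithm to be more efficient, the following criteria must both be fulfilled". The criteria are:

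- "The number of participants without cancer sorted in the category (a) is higher AND"
- "The number of participants with lung cancer sorted into category (b) or (c) is higher"

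Section 5.1.2, item 2, in the statistical part of the Protocol, gives the same pair: "The number of patients without cancer sorted in the category (a) is higher AND" and "The number of patients with lung cancer sorted into category (b) or (c) is higher". The evaluation part of section 6.1.2 states the rule a third time and describes the setting: "A retrospective analysis will compare this algorithm to the PanCan nodule algorithm vs. AI for management efficiency".

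The rule serves an additional objective in section 2.2: "Adding the PanCan algorithm/AI to the LungRads1.1 algorithm for nodule management increases the efficiency". Section 5.2.2 classes all secondary parameters as exploratory. The tests named in section 5.1.1 concern PLCO versus NELSON only.

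The synopsis lists the two counts joined by AND. It does not state the decision rule, and it does not restrict the first count to people without cancer.

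**The concern.** The rule turns two observed counts into a verdict. One extra person on each count is enough. Nothing in it separates a real improvement from sampling variation, although a paired comparison is available because the same participants are sorted twice.

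The Protocol does not leave this decision open. It says three times what suffices. An analyst who follows it as written could report that adding PanCan or AI is more efficient when the data show no more than a coin-toss difference. Nodule-management protocols are also a named component of the cost-effectiveness model (sections 4.2 and 6.1.2), so the label could be carried further than the data justify.

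**Working it through.** **Inputs from the Protocol.** Section 5.3 plans to analyse 5000 screened participants and expects 34 × 5000/2029 × 1.72 = 144.1 CT-detected cancers, which agrees with its stated 144. That leaves 5000 − 144 = 4856 people without cancer. The Protocol gives no error rate, margin, power or discordance figure for this endpoint, so there is no stated result to reproduce.

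**Assumed inputs.** 20 to 500 cancer-free participants sorted differently by the two algorithms (0.4% to 10.3% of 4856), and 4 to 20 cancers sorted differently (2.8% to 13.9% of 144). Under the null the algorithms are equally good, so each disagreement favours either one with probability 0.5, independently.

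**Formula.** Participants sorted alike by both algorithms cancel. Only the m discordant participants decide a count, and the number favouring a given algorithm is Binomial(m, 0.5). Hence

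- m even: P(higher) = [1 − P(tie)]/2
- m odd: no tie is possible, so P(higher) = 0.5

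Cancer and cancer-free participants are different people, so the probability that a given algorithm meets both criteria is the product. The probability that one or the other does is twice that.

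| Discordant cancer-free | Discordant cancers | P(first higher) | P(second higher) | Given algorithm | Either algorithm |
|---|---|---|---|---|---|
| 20 | 4 | 0.412 | 0.312 | 0.129 | 0.257 |
| 200 | 10 | 0.472 | 0.377 | 0.178 | 0.356 |
| 500 | 20 | 0.482 | 0.412 | 0.199 | 0.397 |
| any odd number | any odd number | 0.500 | 0.500 | 0.250 | 0.500 |

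Over the assumed range this gives about 13% to 25% for a given algorithm and 26% to 50% for one or the other. The upper ends need odd counts on both sides.

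**A minimal passing result.** A split of 51 v 50 among discordant cancer-free participants and 6 v 5 among discordant cancers satisfies the rule. The two-sided sign-test p-value is 1.0 on each.

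**Better on one count only.** If one algorithm is clearly better for cancer-free participants and the two are equal for cancers, the first criterion is met almost surely. The rule is then met with the probability of the second criterion alone: 0.31 (4 discordant cancers) to 0.50 (any odd number).

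**The synopsis wording.** Let K be the number of cancers, the same for both algorithms. Let algorithm j place nⱼ cancer-free people in (a) and cⱼ cancers in (b) or (c). Its total in (a) is Tⱼ = nⱼ + K − cⱼ. If T₁ > T₂ and c₁ > c₂, then n₁ − n₂ = (T₁ − T₂) + (c₁ − c₂) > 0. Any result that meets the synopsis counts therefore also meets the section 4.2 criteria.

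**The case against.** The endpoint is exploratory and carries no alpha or power. Section 4.2 can be read as merely defining a term. Section 5.1.2 names no test for the other secondary endpoints either, and a separate SAP, which was not available here, could add intervals. The lead-in that the trial aims to show these objectives covers six of them, some softly worded, and is not a commitment to a hypothesis test. All of this limits the weight of the point. It does not remove it: a missing test can be left to an SAP, but here the Protocol itself fixes what suffices for the verdict.

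Requiring both counts to be higher is a real safeguard. It brings the chance of naming a given algorithm down from about 50% to at most 25%. It also guards against rewarding a mere shift of threshold, because sending more people to routine surveillance then tends to mean fewer cancers in recall or work-up. If the algorithms differ mainly in that way, the rule would be met less often than calculated. This stands, as does the objection that the discordance figures and the symmetric null are assumed.

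Two stronger readings are tempting. A reader might infer that the synopsis, by omitting the cancer-free restriction, lets missed cancers add to an algorithm's score. The algebra above shows that it cannot do so while both counts must be higher: the synopsis version is at least as strict, and the difference is editorial. A reader might also infer that the trial's overall 5% error rate is compromised. Section 5.2.2 places this endpoint outside the controlled hierarchy, so it is not.

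**Conclusion.** The point holds, as a modest one. As written in sections 4.2, 5.1.2 and 6.1.2, the rule can declare an algorithm more efficient on differences that chance readily produces: about 13% to 25% of trials for a given algorithm and 26% to 50% for one or the other. These figures assume equally good algorithms, independent and symmetric disagreements, 20 to 500 discordant cancer-free participants and 4 to 20 discordant cancers. None of these assumptions comes from the Protocol. The conclusion holds across the range, but the sizes are illustrative and would fall under a threshold-type difference. The damage is confined to the interpretation of one exploratory comparison.

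**What to change.** In all three sections, replace the bare verdict with two paired differences between the algorithms: in the share of cancer-free participants placed in (a), and in the share of cancers placed in (b) or (c). Give each a 95% confidence interval for paired proportions. Use the label *more efficient* only if both intervals exclude zero in favour of the same algorithm; otherwise report the two differences descriptively. As an editorial matter, align the synopsis wording of the first count with section 4.2.

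The change needs wording and a standard paired analysis, with no new data. The cost is that the label becomes harder to earn. With an exact one-sided 2.5% test on each count, a given algorithm would be named by chance in at most 2.5% of trials when it is truly better on one count and equal on the other. When the two are equal on both, the figure is about 0.02% to 0.05% (50 to 500 discordant cancer-free participants, 6 to 30 discordant cancers). With fewer than 6 discordant cancers the label is unattainable under such a test: even if all favour one algorithm, 0.5⁵ = 0.031 exceeds 0.025, whereas 0.5⁶ = 0.016 does not. The descriptive report covers that case.
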